24.2 Efficacy Analysis

All patients with measurable disease by RECIST version 1.1 criteria at Baseline who complete at least one post-baseline radiographic assessment or discontinue study medication early due to disease progression will be considered evaluable for efficacy.

Response to treatment according to the RECIST criteria will be reported via descriptive statistics by dose level. The absolute and percent change from baseline for the extent of disease (sum of the longest diameters) will be summarized at each scheduled evaluation using descriptive statistics.

For PVNS patients, the Sponsor will receive radiologic images for possible retrospective analysis of treatment response, to be performed by a central vendor. Methodology of assessment will include RECIST 1.1 and development of other techniques for descriptive and exploratory analysis.

All patients who are eligible for efficacy analyses will be evaluable for progression-free survival, regardless of the presence or absence of measurable disease. Progression-free survival will be calculated for each subject. Progression-free survival is defined as the number of days from the first day of treatment to the date of the first documented disease progression or date of death, whichever occurs first.

For each subject with a response to therapy, duration of response will be calculated. The duration of response is defined as number of days from the date of initial response (confirmed at least 28 days later) to the date of first documented disease progression or death, whichever occurs first. If the information is available, the pre-study stability of disease will also be recorded to assist the interpretation of the on-treatment progression-free survival.

In the event no disease progression or death is documented prior to study termination, analysis cutoff, or the start of confounding anticancer therapy, progress-free survival and duration of response will be censored at the date of last evaluable tumor assessments. In addition, relationships between antitumor activity, pharmacodynamic markers, and drug exposure levels will be explored.

For the malignant effusion cohort, the frequency of effusion removal procedures (e.g., paracentesis or thoracentesis) prior to study entry will be compared to the frequency of on-study fluid removal procedures. The volume of fluid removed by on-study procedures for each patient will be plotted as appropriate. Puncture-free survival ([Seimetz 2011](#)) will be calculated for each patient. Puncture-free survival is defined as the number of days from the first day of treatment to the date of the first need for therapeutic puncture or death.

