Dosage and Regimen	
The proposed starting dose is 200 mg QD. A BID dosing regimen may be used in subsequent cohorts, pending review of the PK from the initial cohort.
 
Cohorts of patients with solid tumors will be enrolled using 100% dose increments in the absence of drug-attributable Grade 2 toxicity. In each cohort (and following the one-week run-in period for applicable patients), the first patient will be observed for at least one week before additional patients in that cohort are treated with pexidartinib. Following the one-week run-in period for applicable patients, upon the occurrence of Grade 2 or greater drug-attributable toxicity, in the absence of dose limiting toxicity (DLT), dose escalation will proceed sequentially by 50% increments. From that point forward, the standard "3+3" design will be used. Following the one-week run-in period for applicable patients, if DLT is observed in one patient at a given cohort, at least 6 patients will be treated at that dose. Following the one-week run-in period for applicable patients, if DLT is observed in 2 or more of 6 patients at a dose level, then the next lower dose level will be expanded or an intermediate dose level will be introduced. The MTD is defined as the dose at which ≤ 1 of 6 patients experience a DLT during Cycle 1, with the next higher dose having at least 2 of the up to 6 patients experiencing a DLT during Cycle 1. If no DLT is observed, the recommended dose for further evaluation will be established based on toxicity, PK, and convenience of dosing in approximately 3–6 patients treated at that dose. Dose escalation will only be permitted if adequate safety and tolerability have been demonstrated at the previous lower dose for 28 days.
 
The dosage for the Extension cohorts will be the RP2D level of 1000 mg/day, using a BID regimen.

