15.0 DISCONTINUATION OF TREATMENT AND WITHDRAWAL OF PATIENTS

The reasons a patient may discontinue or be withdrawn from the study include, but are not limited to, adverse event, disease progression, patient request, protocol violation, patient noncompliance, study termination by the Sponsor, and subject transition to commercial pexidartinib (Turalio™). When a patient discontinues or is withdrawn, the investigator will notify the Sponsor and should perform the procedures indicated in the End of Study visit column in the study flow chart 7–30 days after the last dose of study drug and prior to initiation of any new anti-cancer therapy. Follow-up information will be obtained for patients who discontinue their participation in or are withdrawn from the study. Patients withdrawn from the study will be replaced at the discretion of the medical monitor and the investigator. Test article administration may be discontinued for an adverse event or at the discretion of the investigator.

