For the five disease-specific Extension cohorts, a sample size of 10 patients is considered the minimum sample size required to test the hypothesis that single agent pexidartinib can provide a clinical benefit in this patient population. For each Extension cohort, we plan to test the hypothesis of no clinical benefit against the hypothesis that at least 30% of patients achieve a clinical benefit. With a sample size of 10 patients per group, we will have 85% power at a 0.10 significance level to declare pexidartinib worthy of further study if at least 2 patients achieve clinical benefit. For this study, clinical benefit is defined as either CR/PR or PFS ≥ 6 months. If fewer than 2 patients achieve clinical benefit within a disease group, pexidartinib will not be considered worth of further study within that disease. Depending on the response in the 10-patient cohort, the sample size for a specific cohort may be increased by 30 additional patients (to approximately 40 patients total) if those data are determined to be necessary to design additional studies in that indication.

For the miscellaneous Extension cohort, a sample size of 20 patients will be used, as the tumor types are anticipated to be rare. The sample size is not determined by any statistical power considerations. Accordingly, the potential clinical benefit will be evaluated on a per-patient basis. If one or more partial responses are observed in patients in the miscellaneous cohort, additional patients (up to 20 total additional patients) may be recruited if needed to profile the tumor responses in the specific (or related) indications.

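### Section 24.2 tabulates RECIST response by dose level, which cannot separate the six extension cohorts, and no per-cohort response or benefit estimate with an interval is planned

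*Combined protocol and SAP*

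**What the plan says.** Section 24.2 gives one grouping for tumour response: "Response to treatment according to the RECIST criteria will be reported via descriptive statistics by dose level". It defines a single efficacy population for the whole study, namely patients with measurable disease at baseline "who complete at least one post-baseline radiographic assessment or discontinue study medication early due to disease progression will be considered evaluable for efficacy". Change in the sum of diameters is summarised by visit with no grouping named. PFS and duration of response are calculated per subject.

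Two groups are singled out in 24.2. PVNS patients may have a retrospective central image read. The malignant effusion cohort has fluid-removal frequency and volume, and puncture-free survival. Neither is a response or benefit rate with an interval.

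The Synopsis fixes the extension dose: "The dosage for the Extension cohorts will be the RP2D level of 1000 mg/day, using a BID regimen". Section 9.1 also places all six cohorts at 1000 mg/day. Section 8.1 makes clinical benefit in specific malignancies the extension's primary objective.

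Section 24.6 works by disease. Clinical benefit is CR/PR or PFS of at least 6 months. There are 10 patients per disease-specific cohort, and the negative decision reads "If fewer than 2 patients achieve clinical benefit within a disease group". On expansion it says: "Depending on the response in the 10-patient cohort, the sample size for a specific cohort may be increased by 30 additional patients". The miscellaneous cohort is judged per patient and has its own trigger ("If one or more partial responses are observed in patients in the miscellaneous cohort").

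Section 15.0 adds: "Patients withdrawn from the study will be replaced at the discretion of the medical monitor and the investigator".

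**The concern.** Dose level is a natural grouping for the escalation phase. In the extension phase it is constant by design, so it carries no information about disease. Individual dose reductions under Section 14.7 do not turn it into a proxy for disease. A response table that follows 24.2 as written would put salivary MEC, PVNS, GIST, ATC, effusion and miscellaneous tumours in one row, joined by any escalation patients treated at the same dose.

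Section 24.6 allows a cohort to grow to about 40 patients when the data are needed to design further studies in that disease. A designer would want the rate in that disease, its precision and the denominator behind it. A pass/fail count of 2 gives none of these, and neither does a dose-level row.

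The denominator matters as well. Section 24.6 counts 10 per group without saying whether these are treated or evaluable patients. The 24.2 evaluable set leaves out a patient who stops, for toxicity say, before the first 8-week scan. Such a patient cannot have a documented response, so the omission shortens the denominator and leaves the numerator alone. Discretionary replacement can move the treated number above 10. In an open-label, single-arm setting it is better to settle this before results are seen.

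**Working it through.** **Inputs from the documents.** n = 10 per disease-specific cohort, threshold 2, benefit rate 30%, stated power 85%, significance level 0.10 (all Section 24.6). Expansion to about 40 (Section 24.6). One extension dose, 1000 mg/day (Synopsis, Section 9.1).

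**Assumed inputs.** 3 patients with benefit; 2 patients who stop early without a scan and without progression; a 5% null rate. Section 24.6 describes its null only as no clinical benefit and gives no number.

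**1. The plan's own figure.** P(X ≥ 2) = 1 − (1−p)^N − N·p·(1−p)^(N−1). With N = 10 and p = 0.30: 1 − 0.0282 − 0.1211 = 0.851. The stated 85% is reproduced and is not in dispute.

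**2. The same threshold at other N.**

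| N | P(X ≥ 2) at 30% | P(X ≥ 2) at assumed 5% null |
|---|---|---|
| 8 | 1 − 0.0576 − 0.1977 = 0.745 | – |
| 10 | 0.851 | 1 − 0.5987 − 0.3151 = 0.086 |
| 12 | 1 − 0.0138 − 0.0712 = 0.915 | 1 − 0.5404 − 0.3413 = 0.118 |

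At N = 8 power is 74% (0.7447 before rounding). At N = 12 the chance of passing under a 5% null is 11.8%, above the stated 0.10. The threshold of 2 therefore belongs to N = 10. Even there it keeps to 0.10 only if the null rate is about 5.45% or less.

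**3. Effect of the denominator on a reported rate** (assumed counts, Clopper-Pearson 95% intervals).

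| Denominator | n/N | Rate | 95% CI |
|---|---|---|---|
| All treated, no replacement | 3/10 | 30% | 7–65% |
| 24.2 evaluable set, 2 dropped | 3/8 | 37.5% | 9–76% |
| All treated, the 2 replaced without benefit | 3/12 | 25% | 5–57% |

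The same three patients with benefit give rates 37.5 − 25 = 12.5 points apart.

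**4. Precision available.** At 3, 5 or 8 of 10 the exact interval is 59, 63 or 53 points wide. At 12, 20 or 32 of 40 it is 30, 32 or 27 points wide. For example, 12/40 = 30% has interval 17–47%.

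**The case against.** The strongest reply is that Section 24.6 sits in the same statistical chapter and already gives the cohort as the unit, the endpoint, n, the threshold and the expansion provision. Nobody can apply it without counting benefit within each disease. That stands: the decision rule is intact, and the absence of the composite endpoint from 24.2 is partly a matter of where it is written, since both components are defined there.

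A reader might infer that 24.2 ignores the cohorts altogether. It does not, because it has the effusion analyses and the possible PVNS read. A reader might also infer that no denominator exists. One does: the study-wide evaluable set can be applied within a cohort. What is unstated is whether the 10 in 24.6 are treated or evaluable patients.

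A more dramatic inference is that a pooled row of, say, 10/70 would leave a given 10-patient cohort anywhere from 0/10 to 10/10. The arithmetic is right, but it assumes that the reader sees only that row. The 24.6 counts and the per-subject results make that unrealistic.

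It is also fair that analyses are described as descriptive in general (Section 24.5), that intervals at n = 10 are wide, and that Kaplan-Meier curves for response duration would rest on few patients per cohort. The wide intervals are a reason to show them, because a bare 3/10 looks firmer than it is. The Kaplan-Meier point is accepted, so those summaries are optional.

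**Conclusion.** The point holds in a limited form. Followed as written, the grouping in 24.2 cannot describe response by disease in the extension phase, and no section plans a per-cohort response or clinical-benefit estimate with an interval. The go/no-go decision, the data collected and the 85% power figure at N = 10 are unaffected.

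The denominator effect is real, but its size depends on assumed counts. With 2 of 10 patients lost before a scan, the cohort rate rises by 7.5 points (30% to 37.5%), and the power of the threshold at a 30% rate falls from 85% to 74%. The 8.6% and 11.8% figures rest on an assumed 5% null. This should be corrected, but it does not invalidate the extension design.

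**What to change.** In Section 24.2:

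- Report RECIST response by dose level for the escalation phase and by extension cohort for the extension phase, without pooling the two.
- For each disease-specific cohort give n/N and exact 95% confidence intervals for CR/PR and for the 24.6 clinical-benefit endpoint.
- Take N as all treated patients in the cohort. Give the present evaluable set as a supporting analysis.
- Count replacement patients in the all-treated estimate and state how many there were.
- List the miscellaneous cohort per patient, as 24.6 provides.

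In Section 24.6, state that the threshold of 2 applies to the first 10 treated patients in each disease-specific cohort, because it was set for 10.

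Kaplan-Meier summaries of PFS and duration of response by cohort are optional. They would suit the existing rule that "duration of response will be censored at the date of last evaluable tumor assessments".

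The cost is a few sentences and a different table grouping, with no new data and no change in sample size. The downsides are intervals of about 53–63 points at 3, 5 or 8 of 10, and somewhat lower rates on all treated patients than on the evaluable set.

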Chemistry, hematology, urinalysis		X		X ⁵	X ⁵	X ⁵	X ⁵ (no urinalysis)	X	
ECG		X		X				X	
Vital Signs		X	X	X	X	X	X (unless remote)	X	
Plasma for PK ⁶			X	X	X	X			
Pregnancy Test ⁷		X						X	
ECOG Performance Status Assessment		X			X	X		X	
WOMAC Questionnaire ⁸			X	X	X	X	X (unless remote)	X	
Numeric Rating Scale (NRS) for PVNS Symptoms Questionnaire to Patient ⁸			X	X	X	X	X (unless remote)	X	
Dispense Numeric Rating Scale (NRS) for PVNS Symptoms Questionnaire for Outpatient Completion ⁹		X		X	X	X	X (unless remote)		
Serum and Urine for Biomarker Assessment ¹⁰			X		X				
Radiographic Assessment of Tumor Burden ¹¹		X				X	X (every 6 months)	X	X
Test Article Compliance			X	X	X	X	X (unless remote)	X	
Concomitant Medications		X	X	X	X	X	X	X	
Adverse Events ¹²			X	X	X	X	X	X	
Collection of surgical data ¹³								X	X

C = cycle; D = day; CxDx = Cycle x, Day x; LD = last dose; wk = week

- ¹ Screening window for radiographic assessment of tumor burden is 4 weeks.
- ² If well tolerated and no tumor progression; clinic visits, laboratories at 1-month intervals with radiographic assessment performed every two cycles. Radiographic assessment of tumor status can be performed every four cycles in patients who complete 14 cycles of treatment (i.e., reached Cycle 15 visit) and have Cycle 13 and Cycle 15 MRI scans that indicate SD or better per local RECIST v1.1 reading. For patients beyond Cycle 40, clinic visits will transition to every 12 weeks/3 cycles (remote serum chemistry and hematology as well as a telephone check-in for AEs and con meds and to review remote safety laboratory data may be performed in lieu of an on-site visit for subjects without ongoing Grade 2 or greater related adverse events; regular procedures not performed remotely include Weight, PE, Vitals, WOMAC, NRS, and IP compliance), with on-site visit and radiographic assessments performed every 24 weeks/6 cycles.
- ³ End of Study or early withdrawal procedures should be completed 7-30 days after the last dose of study drug (or on the date of last dose of study drug for all subjects that enroll in the phase 4 continuation study) and prior to the initiation of any new anti-cancer therapy. If patient is starting commercially available drug then the end of study visit should be conducted before that transition.

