14.7.1 Renal Impairment

A reduced dose of 600 mg/day (200 mg in the morning and 400 mg in the evening) is recommended in study subjects with mild to severe renal impairment (creatinine clearance [CL_{cr}] 15 to 89 mL/min estimated by Cockcroft-Gault using actual body weight).

14.8 End of Study/Early Withdrawal (last dose for subjects that enroll in phase 4 continuation study or immediately transition to commercial pexidartinib; last + 30 ± 7 days for all other subjects)

Note: In order to be eligible to participate in the phase 4 PVNS continuation study, subjects must not be withdrawn from PLX108-01 until they are ready to begin screening in the phase 4 continuation study. Screening for the phase 4 continuation study may occur prior to withdrawal from PLX108-01.

Following the last dose of drug, all patients will have the following evaluations:

1. Physical examination including weight (kg) and vital signs (sitting blood pressure, pulse rate, and respiratory rate, and oral temperature [°F]).
2. Standard 12-lead ECG to determine QTcF.
3. Clinical laboratory evaluation (hematology, chemistry, urinalysis, serum pregnancy test (women of child-bearing potential).
4. ECOG Performance status assessment.
5. For patients enrolled after the implementation of Amendment 8, collect the six (6) completed NRS for PVNS Symptoms questionnaires and give the patient another one of the questionnaires to complete predose. NOTE: the NRS for PVNS Symptoms questionnaire to be completed in the clinic is exactly the same as the other 6 daily questionnaires.
6. For patients enrolled after the implementation of Amendment 8, then give the patient the Western Ontario and McMaster Universities Osteoarthritis Index (WOMAC) questionnaire to complete predose. NOTE: At each of the applicable visits, sites should refrain from providing any interpretation of how the questions should be answered by the patient.
7. Radiographic assessment of tumor burden.
8. Test article compliance.
9. Concomitant medications.
10. Collection of surgical data - If surgical resection of the tumor is performed within 30 days of the last dose of study treatment, details of the surgery and its outcome should be obtained.

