14.9 Twelve-week Follow-up (last dose + 12 weeks [+4-week window])

Within +12 weeks (+4 week window) of the last dose of study drug, all patients that don't enroll in the phase 4 continuation study or transition immediately to commercial pexidartinib will have the following study evaluations:

1. Radiographic assessment of tumor burden
2. Collection of surgical data - If surgical resection of the tumor is performed within 12 weeks of the last dose of study treatment, details of the surgery and its outcome should be obtained.

For patients who miss the 30-day and 12-week post-treatment follow-up visit, post-treatment radiographic assessments from any source (e.g., primary care provider) within 24 weeks of last dose are acceptable.

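### In the extension cohorts, the PFS and response-duration censoring rule depends on the start of other anticancer therapy, but no visit is scheduled to record it, and later scans are not excluded

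*Combined protocol and SAP*

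**What the plan says.** Section 24.2 measures PFS from the first day of treatment to progression or death. If neither is "documented prior to study termination, analysis cutoff, or the start of confounding anticancer therapy", then "progress-free survival and duration of response will be censored at the date of last evaluable tumor assessments". It does not define confounding, does not name surgery, and does not limit the last assessment to one made before the other therapy. Change in tumour size is summarised at every scheduled evaluation, with no such limit.

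Section 15.0 places the End of Study procedures 7 to 30 days after last dose and "prior to initiation of any new anti-cancer therapy". Footnote 3 of the extension flow chart says the same: "prior to the initiation of any new anti-cancer therapy". Section 14.8 and the flow chart make this the last visit that records concomitant medications. Sections 18.0 and 26.2 end AE and SAE collection there.

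Section 14.9 then schedules a visit at last dose + 12 weeks (+4) with two items, a scan and surgical data. The second is conditional: "If surgical resection of the tumor is performed within 12 weeks of the last dose of study treatment". If follow-up is missed, "post-treatment radiographic assessments from any source (e.g., primary care provider) within 24 weeks of last dose are acceptable".

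Section 24.6 uses PFS in the decision rule for each disease-specific cohort: "clinical benefit is defined as either CR/PR or PFS" of at least 6 months, with at least 2 of 10 patients needed.

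**The concern.** A censoring rule can be applied only if its trigger date is known. Here the protocol orders events so that, in a compliant patient, new therapy begins after the last scheduled record of treatments, while imaging goes on. Unless the site happens to report the therapy, a clean scan taken during it looks like any other scan and lengthens the patient's PFS or response duration.

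Resection raises a different problem. Its details are collected, but the analysis text does not say what to do with them. Section 10.1 admits PVNS patients whose tumour is resectable only by mutilating surgery, so resection during follow-up is foreseeable. Section 14.8 collects surgery within 30 days of last dose at the same visit as a scan, so even the End of Study scan could follow resection.

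PFS of at least 6 months is one of two routes to clinical benefit in a rule needing two patients out of ten, so one misclassified patient can matter.

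**Working it through.** **1. Records against scans (extension cohorts, time from last dose)**

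| Period | Treatments recorded? | Surgery recorded? | Scan accepted? |
|---|---|---|---|
| End of Study, day 7–30 | Yes (14.8) | Yes, within 30 days (14.8) | Yes |
| To week 12 | No scheduled entry | Yes (14.9) | Yes |
| Weeks 12–16 | No scheduled entry | No | Yes, visit window (14.9) |
| To week 24, if follow-up missed | No scheduled entry | Not after week 12 | Yes, any source (14.9) |

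The longest stretch with scans possible but no scheduled treatment record, ending at week 24 (day 168):
- from an End of Study visit on day 7: 168 − 7 = 161 days;
- from one on day 30: 168 − 30 = 138 days.

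For a scan at exactly 12 weeks after a day-30 visit, it is 84 − 30 = 54 days. The Section 14.8 heading gives 30 ± 7 days instead of 7–30; a day-37 visit leaves 168 − 37 = 131 days.

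**2. Other routes to the date**
- Section 15.0 says information will be obtained after discontinuation, but gives neither content nor timing.
- Section 26.2 follows drug-related AEs, SAEs and other reportable information until, among other end points, another anticancer treatment begins. Sites would know that date only for patients with such an event still open.
- The 12-week visit lists no vital-status item, although death is a PFS event.

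**3. Which outcomes are exposed**
- Best overall response: Attachment 4 limits it to the period until end of treatment, so it is protected.
- PFS and duration of response: no end-of-treatment limit, so both are exposed.
- Change in tumour size: summarised at each scheduled evaluation, which includes the 12-week scan, so it is exposed.

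Attachment 4 itself asks protocols to state how new therapy before progression affects best response and whether post-treatment assessments count. Section 24.2 states neither.

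**4. The plan's own figure**

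Inputs from Section 24.6: n = 10, success if X ≥ 2, true rate 30%, stated power 85%, level 0.10.

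P(X ≥ 2) = 1 − (1 − p)^10 − 10p(1 − p)^9

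At p = 0.30: 1 − 0.0282 − 0.1211 = 0.851, which reproduces 85%. No null rate is given. The level equals 0.10 at p = 0.0545, so a null near 5% fits, but that is an assumption.

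**5. Illustration: one patient falsely credited**

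The remaining nine patients need only one success: P = 1 − (1 − p)^9.

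| Assumed true rate p | Rule as planned | One falsely credited |
|---|---|---|
| 0.01 | 0.004 | 0.086 |
| 0.05 | 0.086 | 0.370 |
| 0.10 | 0.264 | 0.613 |

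Two such patients meet the rule outright. These figures are conditional on the misclassification having happened; the documents give no basis for its probability.

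**The case against.** The strongest reply is that the plan intends the opposite of what is feared. Section 24.2 makes confounding therapy a censoring trigger and once describes PFS as on-treatment. A reader might infer that scans on another drug or after surgery are counted as benefit. The documents do not say so. What stands is narrower: such scans can be counted, because nothing scheduled identifies the therapy and nothing in the text removes the scan.

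A reader might also infer that the start date is never collected. The CRF is not among the documents, and Sections 15.0 and 26.2 may yield the date for some patients. The supportable statement is that no scheduled entry exists. Resection is different again: it is recorded to week 12, and the gap is its missing role in the analysis and the uncovered weeks after that.

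It is tempting to size the problem by the shortest dosing compatible with PFS of 6 months (taken as 183 days): 183 − 112 = 71 days with a 16-week scan, or 183 − 168 = 15 days with a 24-week scan. Those figures follow from the PFS definition whether or not another therapy was given, so they do not measure this defect.

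Reach is limited too. Patients who stop for progression already have their event. Those who move to the phase 4 study or commercial drug have no 12-week visit. The synopsis ties post-treatment imaging to PVNS, whereas Section 14.9 covers all remaining patients, so exposure outside PVNS is unsettled. Outside scans need missed follow-up: both visits in Section 14.9, either one in flow-chart footnote 4.

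Finally, Section 24.5 calls the analyses generally descriptive. That lowers the stakes, but Section 24.6 still attaches a development decision to the count.

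**Conclusion.** The concern holds for extension patients who stop without progression and do not move to the phase 4 study or commercial drug. For them, the start of later systemic therapy has no scheduled record. Resection is recorded to week 12 but has no stated effect, and neither the censoring date nor the size-change summary is confined to scans before such therapy. A clean later scan lengthens recorded PFS or response duration, and a removed lesion can appear as shrinkage; both favour the drug.

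The frequency is unknown. The shift in the 2-of-10 rule is an illustration that assumes one false success and a true benefit rate of 1% to 10%. The case for acting now is practical: a date that was not collected may not be recoverable at analysis.

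**What to change.** **Data collection (Section 14.9 and the 12-week flow-chart column).** At the 12-week visit, and whenever a post-treatment scan up to 24 weeks is accepted, record:
- vital status, with date of death;
- start date and type of any new anticancer therapy;
- date of any resection or radiotherapy of the study tumour.

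Fields at the 12-week visit alone would not be enough: outside scans come from patients who missed follow-up, and therapy may start between weeks 12 and 24.

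**Analysis (Section 24.2).** State that:
- resection or radiotherapy of the study tumour counts as confounding therapy;
- PFS and duration of response are censored at the last evaluable assessment before confounding therapy starts;
- later scans, including outside scans, are not used for PFS, duration of response or percent change.

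**Cost.** A few CRF fields, a query to the site when an outside scan is accepted, and a short change to Section 24.2. Some PFS times and benefit counts will become less favourable.
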